10.14. Appendix 14: Management for Immune-Related Adverse Events

Gastrointestinal irAEs		
Severity of Diarrhea/Colitis (NCI-CTCAE v5.0)	Initial Management	Follow-up Management
K;rade 1 IDian-hea: <4 stools/day over baseline Colitis: asymptomatic	Continue study treatment Symptomatic treatment (eg [operarnide])	Close monitoring for worsening symptoms. Educate participant to report worsening immediately. If worsens: Treat as Grade 2, 3 or -
K;rade 2 IDian-hea: 4 to 6 stools per day over Baseline; IV fluids indicated <24 hours; Mt interfering with ADL Colitis: abdominal pain; blood in stool	Withhold study treatment Symptomatic treatment	If improves to Grade 1: Resume study treatment. If persists >5-7 days or recurs: Treat as Grade 3 or 4.
K;rade 3 to 4 PiaThea (Grade 3): 7 stools per day over Baseline; incontinence; IV fluids 24 hours; interfering with ADL Colitis (Grade 3): severe abdominal pain, medical intervention indicated, peritoneal signs K;rade 4: life-threatening, perforation	Withhold for Grade 3 Permanently discontinue study treatment for Grade 4 or recuITent Kirade 3 1.0 to 2.0 mg/kg/day prednisone IV or equivalent Add prophylactic antibiotics for opportunistic infections Consider lower endoscopy	If improves: Continue steroids until Kn-ade 1, then taper over at least 1 month; resume study treatment following steroids taper (for initial Kn-ade 3). If worsens, persists >3 to 5 days, or recurs after improvement. Add infliximab 5 mg/kg (if no contraindication). -Note: infliximab should not be used in cases of perforation or sepsis.

Dermatological irAEs		
Grade of Rash (NCI-CTCAE v8.0)	Initial Management	Follow-up Management
Grade 1 to 2 Covering 90% body surface area	Continue study treatment Symptomatic therapy (for example, antihistamines, topical steroids)	If persists > 1 to 2 weeks or recurs: Withhold study treatment Consider skin biopsy Consider 0.5-1.0 mg/kg/day prednisone or equivalent. Once improving, taper steroids over at least 1 month, consider prophylactic antibiotics. If for opportunistic infections, and reswne study treatment following steroids taper. If worsens: Treat as Grade 3 to 4.
Grade 3 to 4 Grade 3: Covering >30% body surface area; Grade 4: Life threatening consequences	Withhold study treatment for Grade 3 Permanently discontinue for Grade 4 or reswne to Grade 3 Consider skin biopsy Dermatology consult 1.0 to 2.0 mg/kg/day prednisone or equivalent Add prophylactic antibiotics for opportunistic infections	If improves to Grade I: Taper steroids over at least 1 month; reswne study treatment following steroids taper (for initial Grade 3).

Pulmonary irAEs		
Grade of Pneumonitis (NCI-CTCAE v5.0)	Initial Management	Follow-up Management
Grade 1 !Radiographic changes only	Consider withholding study treatment Monitor for symptoms every 2 to 3 days Consider Pulmonary and Infectious Disease consults	Re-assess at least every 3 weeks. If worsens: Treat as Grade 2 or Grade 3 to 4.
Grade 2 Mild to moderate new symptoms	Withhold study treatment Pulmonary and Infectious Disease consults Monitor symptoms daily; consider hospitalization 1.0 to 2.0 mg/kg/day prednisone or equivalent Add prophylactic antibiotics for opportunistic infections Consider bronchoscopy, lung biopsy	Re-assess every 1 to 3 days If improves: When symptoms return to Grade ::1, taper steroids over at least 1 month, and then resume study treatment following steroids taper. If not improving after 2 weeks or worsening: Treat as Grade 3 to 4.
Grade 3 to 4 Kirade 3: Severe new symptoms; New/worsening hypoxia; Kirade 4: Life-threatening	Permanently discontinue study treatment. Hospitalize Pulmonary and Infectious Disease consults 1.0 to 2.0 mg/kg/day prednisone or equivalent Add prophylactic antibiotics for opportunistic infections Consider bronchoscopy, lung biopsy	If improves to Grade ::1: Taper steroids over at least 1 month. If not improving after 48 hours or worsening: Add additional immunosuppression (for example, infliximab, cyclophosphamide, IV immunoglobulin, or mycophenolate mofetil).

Hepatic irAEs		
Grade of Liver Test Elevation (NCI-CTCAE v5.0)	Initial Management	Follow-up Management
Grade 1 KJgrade I AST or ALT >ULN to . .0x ULN and/or Total bilimbin ULN to 1.5 x ULN	Continue study treatment	Continue liver function monitoring If worsens: Treat as Grade 2 or 3 - 4.
Grade 2 ST or ALT >3.0 to 5 x ULN and/or total bilimbin >1.5 to 3 x IULN	Withhold study treatment Increase frequency of monitoring o evely 3 days	If returns to Grade 1 : Resume routine monitoring; resume study treatment. If elevation persists >5 to 7 days or worsens: Treat as Grade 3 to 4.
Grade 3 to 4 ST or ALT >5 x ULN and/or total bilimbin >3 x ULN	Pennantly discontinue study reatment Increase frequency of monitoring o evely 1 to 2 days 1.0 to 2.0 mg/kg/day prednisone or equivalent Add prophylactic antibiotics for opportunistic infections Consult gastroenterologist/ hepatologist Consider obtaining MRI/CT scan of liver and liver biopsy if clinically wa1rnted	If returns to Grade 1 : Taper steroids K>ver at least 1 month. If does not improve in >3 to 5 days, worsens or rebounds: Add niycophenolate mofetil 1 gram (g) tv.ice klaily. If no response within an additional 3 to 15 days, consider other immunosuppressants per local iguidelines.

Renal irAEs		
Grade of Creatinine Increased (NCI-CTCAE v8.0)	Initial Management	Follow-up Management
K;rade 1 K=:reatinine increased >ULN to 1.5 x IULN	Continue study treatment	Continue renal function monitoring. If worsens: Treat as Grade 2 o 3 or 4.
K;rade 2 to3 t:reatinine increased >1.5 and ::;6 x IULN	Withhold study treatment Increase frequency of monitoring to every 3 days 1.0 to 2.0 mg/kg/day prednisone or equivalent. Add prophylactic antibiotics for opportunistic infections Consider renal biopsy	If returns to Grade ::;1: Taper steroids over at least 1 month, and resume study treatment following steroids taper. If worsens: Treat as Grade 4.
K;rade 4 K=:reatinine increased >6 x ULN	Permanently discontinue study treatment Monitor creatinine daily 1.0 to 2.0 mg/kg/day prednisone or equivalent. Add prophylactic antibiotics for opportunistic infections Consider renal biopsy Nephrology consult	If returns to Grade ::;1: Taper steroids over at least 1 month.

Cardiac irAEs		
Myocarditis	Initial Management	Follow-up Management
New onset of cardiac signs or symptoms and / or new laboratory CCI [REDACTED] or cardiac imaging abnormalities suggestive of myocarditis	
Withhold study treatment
 
Hospitalize
 
In the presence of life threatening cardiac decompensation, consider transfer to a facility experienced in advanced heart failure and arrhythmia management
 
Consult cardiologist to establish etiology and rule-out immune-mediated myocarditis
 
Guideline based supportive treatment as per cardiology consult*
 
Consider myocardial biopsy if recommended per cardiology consult
	
If symptoms improve and immune-mediated etiology is ruled out, re-start study treatment.
 
If symptoms do not improve/worsen, viral myocarditis is excluded, and immune-mediated etiology is suspected or confirmed following cardiology consult, manage as immune-mediated myocarditis.

none-mediated myocarditis	
Permanently discontinue study treatment
 
Guideline based supportive treatment as appropriate as per cardiology consult.* 1.0 to 2.0 mg/kg/day prednisone or equivalent
 
Add prophylactic antibiotics for opportunistic infections
	
Once improving, taper steroids over at least 1 month.
 
If no improvement or worsening, consider additional immunosuppressants (eg, azathioprine, cyclosporine A).

*Local guidelines, or eg, ESC or AHA guidelines

ESC guidelines website: <https://www.escardio.org/Guidelines/Clinical-Practice-Guidelines>

AHA guidelines website:

<http://professional.heart.org/professional/GuidelinesStatements/searchresults.jsp?q=&y=&t=1001>

Endocrine irAEs		
Endocrine Disorder	Initial Management	Follow-up Management
Grade 1 or Grade 2 endocrinopathies (hypothyroidism, hyperthyroidism, adrenal insufficiency, type I diabetes mellitus)	
 -Continue study treatment -Endocrinology consult if needed -Start thyroid hormone replacement therapy (for hypothyroidism), anti-thyroid treatment (for hyperthyroidism), corticosteroids (for adrenal insufficiency) or insulin (for Type I diabetes mellitus) as appropriate -Rule-out secondary endocrinopathies (ie, hypopituitarism / hypophysitis) 	
 -Continue hormone replacement/suppression and monitoring of endocrine function as appropriate.
Grade 3 or Grade 4 endocrinopathies (hypothyroidism, hyperthyroidism, adrenal insufficiency, type I diabetes mellitus)	
 -Withhold study treatment -Consider hospitalization - Endocrinology consult -Start thyroid hormone replacement therapy (for hypothyroidism), anti-thyroid treatment (for hyperthyroidism), corticosteroids (for adrenal insufficiency) or insulin (for type I diabetes mellitus) as appropriate -Rule-out secondary endocrinopathies (ie, hypopituitarism / hypophysitis) 	
 -Resume study treatment once symptoms and/or laboratory tests improve to Grade ≤ 1 (with or without hormone replacement/suppression). -Continue hormone replacement/suppression and monitoring of endocrine function as appropriate.
Hypopituitarism/ Hypophysitis (secondary endocrinopathies)	
 -If secondary thyroid and/or adrenal insufficiency is confirmed (ie, subnormal serum FT4 with inappropriately low TSH and/or low serum cortisol with inappropriately low ACTH): -Refer to endocrinologist for dynamic testing as indicated and measurement of other hormones (FSH, LH, GH/IGF-1, PRL, testosterone in men, estrogens in women) -Hormone replacement/suppressive therapy as appropriate -Perform pituitary MRI and visual field examination as indicated -If hypophysitis is confirmed: -Continue study treatment if mild symptoms with normal MRI. Repeat the MRI in 1 month -Withhold study treatment if moderate, severe or life-threatening symptoms of hypophysitis and/or abnormal MRI. Consider hospitalization. Initiate corticosteroids (1 to 2 	
 -Resume study treatment once symptoms and hormone tests improve to Grade ≤ 1 (with or without hormone replacement). -In addition, for hypophysitis with abnormal MRI, resume study treatment only once shrinkage of the pituitary gland on MRI/CT scan is documented. -Continue hormone replacement/suppression therapy as appropriate.

Endocrine irAEs		
Endocrine Disorder	Initial Management	Follow-up Management
	
1 mg/kg/day prednisone or equivalent) followed by corticosteroids taper during at least 1 month
 
Add prophylactic antibiotics for opportunistic infections
	

Other irAEs (not described above)		
Grade of other irAEs <NCI-CTCAE v5.0)	Initial Management	Follow-up Management
Grade 2 or Grade 3 clinical signs or symptoms suggestive of a potential irAE	
 -Withhold study treatment pending clinical investigation 	
 -If irAE is ruled out, manage as appropriate according to the diagnosis and consider restarting study treatment -If irAE is confirmed, treat as Grade 2 or 3 irAE.
Grade 2 irAE or first occurrence of Grade 3 irAE	
 -Withhold study treatment -1.0 to 2.0 mg/kg/day prednisone or equivalent -Add prophylactic antibiotics for opportunistic infections -Specialty consult as appropriate 	
 -If improves to Grade ::SI: -Taper steroids over at least 1 month and resume study treatment following steroids taper.
Recurrence of same Grade 3 irAEs	
 -Permanently discontinue study treatment -1.0 to 2.0 mg/kg/day prednisone or equivalent -Add prophylactic antibiotics for opportunistic infections -Specialty consult as appropriate 	
 -If improves to Grade ::;1 : -Taper steroids over at least 1 month.
Grade 4	
 -Permanently discontinue study treatment -1.0 to 2.0 mg/kg/day prednisone or equivalent and/or other immunosuppressant as needed -Add prophylactic antibiotics for opportunistic infections -Specialty consult 	
 -If improves to Grade ::;1 : -Taper steroids over at least 1 month.
Requirement for 10 mg per day or greater prednisone or equivalent for more than 12 weeks for reasons other than hormonal replacement for adrenal insufficiency	
 -Permanently discontinue study treatment -Specialty consult 	
Persistent Grade 2 or 3 irAE lasting 12 weeks or longer		

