 - c. Hemoglobin $\geq 9 \text{ g/dL}$. Limited transfusions to reach this value are allowed, after discussion with the sponsor's medical monitor. There should not be chronic need for transfusions (>1 per month) in the recent (approximately 3 months) past.
7. Adequate renal function, including:
 - d. Estimated creatinine clearance $\geq 50 \text{ mL/min}$ as calculated by Cockcroft-Gault method. In equivocal cases, a 24-hour urine collection test can be used to estimate the creatinine clearance more accurately.

8. Adequate liver function, including:
 - a. Total serum bilirubin $\leq 1.5 \times$ ULN;
 - b. AST and ALT $\leq 2.5 \times$ ULN; $\leq 5.0 \times$ ULN if there is liver involvement by the tumor;
 - c. Alkaline phosphatase $\leq 2.5 \times$ ULN ($\leq 5 \times$ ULN in case of bone metastasis).
9. Adequate coagulation function, including:
 - a. INR or aPTT $\leq 1.5 \times$ ULN.
10. LVEF $\geq 50\%$ by echocardiogram or MUGA.
11. Resolved acute effects of any prior therapy to baseline severity or CTCAE Grade ≤ 1 except for AEs not constituting a safety risk by investigator judgment.
12. Willing and able to comply with all scheduled visits, treatment plan, laboratory tests, lifestyle considerations, and other study procedures.
13. Capable of giving signed informed consent as described in [Appendix 1](#), which includes compliance with the requirements and restrictions listed in the ICD and in this protocol.

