6.6.1. Dosing Interruptions

Appropriate follow-up assessments should be done until adequate recovery occurs as assessed by the investigator. Doses may be held up to 4 weeks until toxicity resolution. Depending on when the AE resolved, a treatment interruption may lead to the participant missing one or more of the subsequent planned doses.

Criteria required before treatment can resume are described in Dose Delays (Section 6.6.2), ISR [Section 8.2.10](#), IRRs ([Appendix 15](#)) or in the specific toxicity management guidelines for CRS ([Appendix 9](#)), and irAEs ([Appendix 14](#)).

The need for a dose reduction at the time of treatment resumption should be based on the criteria defined in [Section 6.6.3](#), unless expressly agreed otherwise following discussion between the investigator and the sponsor.

In the event of a treatment interruption lasting >4 weeks, treatment resumption will be decided in consultation with the sponsor.

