6.6.2. Dose Delays

Re-treatment following treatment interruption for treatment-related toxicity may not occur until all of the following parameters have been met:

- ANC $\geq 1,000/\text{mm}^3$.
- Platelet count $\geq 50,000/\text{mm}^3$
- Nonhematologic toxicities have returned to baseline or Grade ≤ 1 severity (or, at the investigator's discretion, Grade ≤ 2 if not considered a safety risk for the participant).

If a treatment delay results from worsening of hematologic or biochemical parameters, the frequency of relevant blood tests should be increased as clinically indicated.

If these conditions are met within 4 weeks of treatment interruption, PF-07209960 may be resumed. Refer to the Section 6.6.3 for AEs requiring dose reduction at the time of treatment resumption.

If participants require discontinuation of PF-07209960 for more than 4 weeks from last dose (2 missed dose) at any time during the study, then study treatment should be permanently discontinued, unless the investigator's benefit/risk assessment suggests otherwise after discussion with the sponsor's medical monitor.

If a treatment interruption continues beyond Day 28 of the current cycle, then the day when treatment is restarted will be counted as Day 1 of the next cycle.

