6.6.3. Dose Reductions

Following dosing interruption or cycle delay due to toxicity, the PF-07209960 dose may need to be reduced when treatment is resumed.

No specific dose adjustments are recommended for Grade 1/2 treatment-related toxicity. However, participants experiencing recurrent and intolerable Grade 2 toxicity may resume dosing at the next lower dose level based on investigator's medical judgment once recovery to Grade ≤ 1 or baseline is achieved.

Dose reduction of PF-07209960 by 1 dose level (with maximum reduction to dose level -1, 0.3 mg SC, 0.06 mg IV) ([Table 2](#)) will be allowed depending on the type and severity of toxicity encountered. Participants requiring more than 1 dose reduction will be discontinued from the treatment and entered into the follow-up phase, unless otherwise agreed between the investigator and the sponsor. All dose modifications/adjustments must be clearly documented in the participant's source notes and CRF.

Once a dose has been reduced for a given participant, all subsequent cycles should be administered at that reduced dose level, unless further dose reduction is required. Intraparticipant dose re-escalation may be allowed after discussion between the investigator and sponsor. Participant must not experience a Grade 2 or higher adverse event to be eligible for intraparticipant dose re-escalation.

Table 3. Available Dose Reduction Levels From Starting Dose

Dose Level ^a	SC	IV ^b
Starting	CC1	

a. PF-07209960 dose de-escalation below -1 dose level is not allowed.

b. IV infusion over 1 hour (± 10 minutes)

Participants experiencing a DLT may resume dosing at the next lower dose level (if applicable) once adequate recovery is achieved, and in the opinion of the investigator and sponsor, the participant is benefiting from therapy.

For management of immune-related adverse events, please refer to [Appendix 14](#). For all other toxicities, recommended dose reductions for study intervention are described in Table 4.

Table 4. Treatment Dose Modifications for Study Intervention-Related Toxicity

Toxicity	Grade 1	Grade 2	Grade 3	Grade 4

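### The Appendix 14 hepatic irAE table has no baseline provision, although inclusion criterion 8b admits participants with liver involvement at AST/ALT above 3 and up to 5 × ULN

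*Protocol*

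**What the plan says.** Protocol Section 5.1, criterion 8b, sets the AST/ALT entry limit at 2.5 × ULN and raises it to 5.0 × "ULN if there is liver involvement by the tumor".

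The hepatic table in Appendix 14 (Section 10.14) grades by multiples of ULN only:

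- **Grade 2 row** (AST/ALT above 3.0 and up to 5 × ULN): withhold treatment. On recovery, "If returns to Grade 1 : Resume routine monitoring; resume study treatment". Otherwise, "If elevation persists >5 to 7 days or worsens: Treat as Grade 3 to 4".
- **Grade 3 to 4 row** (AST/ALT above 5 × ULN): discontinue permanently and give prednisone 1.0 to 2.0 mg/kg/day. The taper condition is "If returns to Grade 1 : Taper steroids".

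The general re-treatment rule in Section 6.6.2 opens with "Re-treatment following treatment interruption for treatment-related toxicity may not occur until all of the following parameters have been met". Its nonhematologic condition is "Nonhematologic toxicities have returned to baseline or Grade" 1 or lower, with Grade 2 or lower allowed at the investigator's discretion if it is not a safety risk.

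On routing, Section 6.6.1 places the restart criteria in 6.6.2 "or in the specific toxicity management guidelines for CRS" and irAEs. Section 6.6.3 says "For management of immune-related adverse events, please refer to" Appendix 14, and sends all other toxicities to Table 4.

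**The concern.** Criterion 8b deliberately admits people whose ordinary AST/ALT already lies in the Appendix 14 Grade 2 band. For them, the Grade 1 target is not a return to where they started; it is an improvement on it. The table says nothing about this case.

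Two consequences follow if the table is applied as written. A participant whose liver enzymes have fully recovered to baseline does not meet the restart condition. Staying at baseline can also look like an elevation that persists beyond 5 to 7 days, which moves the participant to the row with permanent discontinuation and high-dose prednisone. Once there, the taper condition again asks for a value below baseline.

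What is at stake is the handling of individual participants and consistency between sites, for an event that Section 8.3.8 lists as being of special interest. Dose-escalation inference and the response analysis are not in question.

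**Working it through.** The plan states no figure on this point, so there is nothing to reproduce. The check compares thresholds and the wording of the rules.

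**Inputs**

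- Entry limits (Section 5.1, criterion 8): AST/ALT 2.5 × ULN, or 5.0 × ULN with liver involvement; total bilirubin 1.5 × ULN.
- Appendix 14 hepatic Grade 2: AST/ALT above 3.0 and up to 5 × ULN; total bilirubin above 1.5 and up to 3 × ULN. Grade 3 to 4 starts above 5 × ULN for AST/ALT.
- Grade 1 ceiling for AST/ALT: not legible in the extracted text. I take 3.0 × ULN because Grade 2 starts immediately above it.

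**Step 1: who is affected.** With liver involvement, the entry limit of 5.0 overlaps the Grade 2 band. Without it, the limit of 2.5 lies below 3.0, so there is no overlap. For bilirubin, the entry limit of 1.5 equals the point above which Grade 2 starts, so there is no overlap. Only AST/ALT with liver involvement matters.

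**Step 2: size of the gap.** For baseline *b* in multiples of ULN, the fall below baseline needed to reach Grade 1 is 1 − 3/*b*. The largest rise that stays in the Grade 2 row is 5/*b* − 1.

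| Baseline (× ULN) | Fall below baseline needed | Largest rise still in Grade 2 row |
|---|---|---|
| 3.5 | 1 − 3/3.5 = 14% | 5/3.5 − 1 = 43% |
| 4.0 | 1 − 3/4.0 = 25% | 5/4.0 − 1 = 25% |
| 4.5 | 1 − 3/4.5 = 33% | 5/4.5 − 1 = 11% |
| 5.0 | 1 − 3/5.0 = 40% (taper only) | 5/5.0 − 1 = 0% |

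The restart question arises for baselines above 3.0 and below 5.0 × ULN with a peak no higher than 5 × ULN. From 5.0 any rise enters the Grade 3 to 4 row, where restart does not arise and only the taper condition applies.

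**Step 3: an example.** Baseline is 4.0 × ULN. AST/ALT rises to 4.8 (4.8/4.0 − 1 = 20%), does not settle with supportive care, has no clear alternative explanation, and is managed as a hepatic irAE with dosing held. It then returns to 4.0. Appendix 14 restart needs 3.0, so the condition is unmet. If the value stays at 4.0 for more than 5 to 7 days, the persistence rule can be read as triggered.

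**Step 4: which rule governs.** Section 6.6 directs suspected irAEs to Appendix 14, Section 6.6.1 names Appendix 14 as the source of irAE restart criteria, and Section 6.6.3 separates irAEs from all other toxicities. For an event managed as an irAE, Appendix 14 applies.

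**Step 5: comparison with other rules.**

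| Place | Baseline accepted? |
|---|---|
| 6.6.2, re-treatment | Yes |
| Table 4, nonhematologic Grade 3 and 4 | Yes |
| 4.3.3, Grade 3 irAE DLT criterion | Yes |
| Appendix 14, hepatic restart and taper | No |

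Appendix 6 also scales its AST/ALT limits to an abnormal baseline, but it identifies potential drug-induced liver injury and is not a restart benchmark.

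**The case against.** A reader might infer that Appendix 14 contradicts Section 6.6.2 and that the protocol leaves the winner open. The documents do not support that. Routing of irAEs to Appendix 14 is stated in three places, and only an explicit override sentence is missing. Section 6.6.2 sets conditions that must be met before re-treatment and then permits resumption without requiring it, so applying the stricter appendix breaches nothing. It is also silent on steroids, so the taper condition cannot conflict with it. The hold in the example itself comes from Appendix 14, because Table 4 continues dosing at Grade 2; taking the hold from one rule and the restart from the other would be selective.

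The best case for leaving the text alone goes further. Grade 1 recovery is the usual target in Appendix 14, not a hepatic oddity. Caution is defensible in a first-in-human study of an IL-15 fusion, given the ALT/AST dose-limiting toxicities reported with recombinant IL-15 in Section 2.2.4. Returning to Grade 1 can be read as presupposing a start at or below Grade 1, and persistence as referring to the event's own elevation. Safeguards exist: Section 6.6 sends only selected toxicities without a clear alternative explanation to Appendix 14, and liver metastases may be that explanation; Section 10.3.1 excludes anticipated fluctuation from adverse events; Section 8 requires discussion of safety issues with the sponsor.

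Most of this stands, and it makes the case uncommon. It does not supply the missing term. The safeguards limit who reaches the table, not what the table says on arrival, and Section 8 also disallows protocol waivers, so relying on case-by-case departure is weaker than correct wording. The sensible reading of persistence is the one that the footnote proposed below would state.

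**Conclusion.** The concern holds as a gap in Appendix 14: the hepatic table has no baseline provision for a group that the eligibility criteria admit. Read as written, restart and steroid taper require AST/ALT 14%, 25% and 33% below the participant's own baseline from 3.5, 4.0 and 4.5 × ULN, and values at baseline could be taken as persisting Grade 2 elevation. A stronger reading, that these participants face an absolute bar to restart, is not supported: the event must first be managed as a hepatic irAE, and restart remains open if values reach Grade 1.

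The percentages rest on the inferred 3 × ULN ceiling. The documents do not give the share of participants enrolled above 3 × ULN, so no count is offered. The stop limit of 5 × ULN and the DLT classification are not challenged, and no effect on the MTD or ORR analysis is claimed. This is an optional, low-priority correction, held with medium confidence.

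**What to change.** In the Appendix 14 hepatic table:

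1. Change the Grade 2 resume condition and the Grade 3 to 4 steroid-taper condition to: *Grade 1, or baseline if baseline AST/ALT was >3 × ULN because of liver involvement*.
2. Add a footnote: *for these participants, the >5 to 7 day persistence rule applies only to elevation above baseline*.
3. Leave the >5 × ULN stop limit as it is.

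The cost is a short phrase in two cells and one footnote at the next amendment. Baseline AST/ALT is already collected, so no new data are needed. The downside is slightly less conservative handling of participants with high baseline values.
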